One hundred and fifty treatment seeking alcohol dependent individuals (men and women) will be recruited to participate in this medication study. Subjects may or may not participate in laboratory sessions. Subjects will be recruited through flyers and advertisements in local newspapers and from community substance abuse treatment facilities. Subjects will participate in an initial screening and intake session to obtain informed consent, followed by physical examination and blood work to determine eligibility. Subjects will be randomized to Prazosin (PRZ) or placebo (PLA) and medication will be dispensed in a three times daily dosing schedule (t.i.d. dosing) with 5 mg in the morning, 5 mg in the afternoon and 6 mg at night reached at the end of the 2-week period, and maintained at this or their highest tolerated dose until week 11, followed by a 5-day taper in week 12, as in previous research. The titration schedule was as follows: 1 mg dose at bedtime for 2 nights, followed by a 1mg dose morning and night (8 AM/8 PM) on day 3, then 2 mg dose t.i.d., on days 4-6, 3 mg dose (2 pills each) morning and afternoon, and 4 mg dose (2 pills) at night for days 7-9, increased to 4 mg dosing t.i.d. on days 10-13, and from day 14 through week 11, 5 mg (1 pill) each in the morning and afternoon, and 6 mg for the night (2 pills) dose. Subjects will be maintained on this dose during the laboratory sessions (if completing the laboratory sessions) and until week 12 of the study at which point they will be tapered off the study medication over the course of five days. Some subjects may be tapered prior to completion of the 12 weeks. This taper is similar to what has been used with lofexidine in opiate withdrawal protocols (Bearn et al., 1996; Strang et al., 1997) and in our outpatient relapse prevention study of lofexidine with opiate dependent patients. We expect most subjects will tolerate a daily dose of 16.0mg. However, subjects who cannot tolerate a dosing schedule of 16.0 mg will meet with the study psychiatrist to discuss a reduction in dose down to 10mg/day. Based on the Physician Desk Reference (2007), which reports that dosage may be as high as 40mg daily, we anticipate that 16.0mg per day will be well tolerated by subjects. Subjects who cannot tolerate a minimum dose of 6mg/day will be removed from the study protocol.

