with medication and alcohol withdrawal/anxiety, we used a conservative effect size of $d = .60$ for detection of significant main effects and possible interactions in the clinical trial. At this effect size and power = .80, with $p < .05$, sample size estimates from Cohen (1988, p.258) indicated that we would require 25 subjects per cell to adequately assess the proposed hypotheses for the clinical trial (total $N = 100$). Including a 15-20% drop-out after enrollment, we estimated recruitment of 120 AD patients into the trial to ensure adequate power for the trial.

Data Analysis for Laboratory Study: Repeated measures ANOVA and mixed model procedures to assess treatment group differences in alcohol craving and stress related changes (heart rate, blood pressure, HPA and catecholamine responses) during laboratory exposure to stress and drug cues as compared to neutral imagery conditions. Non-parametric tests will be used to assess occurrence of side effects, treatment retention rates, alcohol use measures, CIWA scores and perceived stress scores during the outpatient treatment phase. The number and type of AE's for the two treatment groups will be conducted using t-tests, chi-square tests and ANOVAs as appropriate. Findings will be used to estimate effect sizes for the medication and guide the larger randomized clinical trial.

Data Analysis for the 12-week clinical trial Study: For this phase, the following moderator and primary and secondary outcomes are specified:

Primary Moderator Measure: Alcohol withdrawal symptoms, as measured by the CIWA alcohol withdrawal scale,

Primary Outcome Measures in the outpatient treatment phase: These are: (1) Heavy drinking days (5 or more for men, 4 or more for women) during the 12 week period, and (2) Any drinking days. Both will be assessed daily using smartphone or interactive voice recording surveys completed by the patients and also with weekly urine drug screens/breathalyzer reports and self report of drug use on the Substance Use Calendar.

Secondary Outcome Measures in the outpatient treatment phase: Secondary outcome measures will include alcohol craving scales, anxiety (Hamilton Anxiety Scale) and depression (CES-D) and sleep quality using the Pittsburgh Sleep Quality Index – PSQI).

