Data Analytic Procedures: Since patients will be randomly assigned to the Prazosin and PLA treatment groups and Intent-to-Treat (ITT) analyses will be conducted for the clinical outcomes. We do not expect the groups to be different on demographic, prior drug use history or other predictor variables. Nevertheless, prior to undertaking the specific analysis for each aim, we will compare the treatment groups on demographic variables, substance use characteristics and previous psychiatric history/predictor variables using t-tests/chi-square analyses as appropriate. If any group differences are found, the specific variable will be entered as a covariate in all of the specific analyses. As there are no established thresholds for AW effects on drinking outcomes in outpatient treatment, baseline AW will be assessed as continuous measure in all overall analyses. Thus, intent-to-treat (ITT) analyses with baseline AW severity (mean-centered continuous CIWA-Ar scores) as a moderator of Time (Pre-Full Dose(FD): weeks 1-2; Post FD: weeks 3-12) were conducted with linear or generalized linear mixed effect (LME/GLME) piecewise growth models for continuous and binary outcomes. Due to a positive skew, number of drinks per day

(AvgD) will be log-transformed. Control variables in all analyses will be gender (0=male), inpatient (0=outpatient), and dropout (0=completer, 1=dropout/withdrawn prior to 4 weeks, 2=dropout/withdrawn after 4 weeks). For secondary outcomes linear mixed models with random intercepts will be used to assess the effect of AW, Treatment and Week (factor 1-12, or Weeks 4, 8 and 12) on the secondary outcome variables. All control variables from the main outcome analyses are included in the secondary outcome analyses. If significant interactions with AW are observed for primary or secondary outcome analyses, a median split of AW scores will be conducted to obtain Low and High AW groups and assess contrasts by treatment.

Aims and Hypotheses for Laboratory and Treatment Outcome Components: All analyses of the laboratory and the treatment components will be based on the following specific aims and hypotheses:

Specific Aim 1: To evaluate the effects of Prazosin on stress-induced alcohol craving and associated neuroadaptations in alcohol dependent individuals. Hypothesis 1: Prazosin will decrease stress-induced alcohol craving and negative emotions in the laboratory as compared to placebo.

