This aim will be tested using mixed model analysis of variance procedures for each of the following dependent measures: VAS alcohol craving scale; VAS anxiety scale; brief CCQ; DES emotions of anger, sadness and fear; heart rate, blood pressure and HPA measures of ACTH and cortisol and NE and EPI.

Specific Aim 2: To evaluate the efficacy of Prazosin versus Placebo in high alcohol withdrawal individuals on primary outcomes of: (a) heavy drinking days (HDD) over 12 week period; (b) Any drinking days (DD%).

Hypothesis 2: In high alcohol withdrawal individuals, Prazosin group will show significant reductions in HDD% and DD% during the 12 week treatment period as compared to Placebo group. No differences between medication treatment groups in the Low alcohol withdrawal individuals will be observed.

Secondary outcome measures such as alcohol craving, Anxiety, depression and sleep quality will be assessed. Findings PSS, COPE and LES scores will be examined.

SECTION VI: RESEARCH INVOLVING DRUGS, BIOLOGICS, RADIOTRACERS, PLACEBOS AND DEVICES
--

If this section (or one of its parts, A or B) is not applicable, state N/A and delete the rest of the section.

A. DRUGS, BIOLOGICS and RADIOTRACERS

1. **Identification of Drug, Biologic or Radiotracer:** What is (are) the **name(s)** of the drug(s) biologic(s) or radiotracer(s) being used? Identify whether FDA approval has been granted and for what indication(s).

Prazosin (marketed by Pfizer Inc) is an alpha-1-adrenergic agonist that is known to preferentially bind to post-synaptic alpha1-adrenergic receptors. Walker et al (2008) found that Prozaosin was effective in suppressing excessive alcohol consumption in rats, suggesting the involvement of the noradrenergic system in alcohol dependence. Simpson et al. (2007) found similar findings in a pilot trial using prozosin for treatment of alcohol dependent men and women. Prazosin therefore is an excellent candidate for treating alcohol seeking behaviors. It may also be more easily tolerated than those medications which directly modulate these transmissions.

All protocols which utilize a drug, biologic or radiotracer **not** approved by, but regulated by, the FDA, or a radiotracer regulated by the RDRC, must provide the following information:

- What is the Investigational New Drug (IND) **number** assigned by the FDA? N/A
- Who holds the IND?
- All protocols which utilize a radiotracer not approved by, but regulated by the FDA must provide the IND number: _____

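### The plan does not say which model term decides Hypothesis 2; if it is a slope interaction, a benefit sustained over the 12 weeks can be missed

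*Combined protocol and SAP*

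**What the plan says.** All places are in Section V of the combined protocol and SAP.

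- **Primary model (item 12, Data Analytic Procedures).** Intent-to-treat analyses take "baseline AW severity (mean-centered continuous CIWA-Ar scores) as a moderator of Time (Pre-Full Dose(FD): weeks 1-2; Post FD: weeks 3-12", using "linear or generalized linear mixed effect (LME/GLME) piecewise growth models for continuous and binary outcomes". No equation, time coding, zero point, random-effects structure or deciding coefficient is given. Treatment is not named in that sentence, although the sentence on secondary outcomes names it.
- **Follow-up step (same paragraph).** "If significant interactions with AW are observed for primary or secondary outcome analyses, a median split of AW scores will be conducted", after which the arms are compared within the Low and High AW groups.
- **Primary endpoints (item 12).** "Heavy drinking days (5 or more for men, 4 or more for women) during the 12 week period, and (2) Any drinking days".
- **Hypothesis 2 (under Specific Aim 2).** In patients with high withdrawal, "Prazosin group will show significant reductions in HDD% and DD% during the 12 week treatment period as compared to Placebo group". For the rest: "No differences between medication treatment groups in the Low alcohol withdrawal individuals will be observed".
- **Basis of the effect size (item 12, Power Analysis).** The pilot figures are mean drinking days per week once full dose was reached: 3.2 on prazosin against 5.5 on placebo. That is a difference in level.
- **Dose course (item 3, Research Plan).** Dose is raised over two weeks, then "maintained at this or their highest tolerated dose until week 11", with a taper in week 12.

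**The concern.** The endpoints, the hypothesis and the pilot effect size all concern how much patients drink over a period. The one term the plan describes concerns change over time. In a growth model, Treatment x AW x slope asks whether the gap between arms widens or narrows within a piece of follow-up. A gap that opens during titration and then holds has a Post-FD slope difference of about zero, yet it is the kind of benefit Hypothesis 2 predicts.

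Two things are at stake. The within-stratum treatment comparisons, which are what Hypothesis 2 states, follow only a significant interaction with AW, so a miss at that step blocks them. And with several candidate terms and two primary outcomes, the deciding test could be chosen after the data are seen.

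**Working it through.** **1. The plan's own figure.** With d = 0.60, power 0.80 and two-sided 5%, n per arm = 2 x (1.96 + 0.84)² / 0.60² = 15.68 / 0.36 = 43.6, so 44, or about 22 per cell of a 2 x 2 design. The plan's 25 per cell (N = 100) is not reproduced exactly but errs on the safe side: 50 v 50 gives about 0.84 for a main effect. This calculation is for a difference in means; it sizes no slope test.

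**2. Assumptions not in the documents.** 120 patients, 60 per arm; 12 weekly values, normal outcome; random intercept variance 0.5; random slope SD 0.05 per week (variance 0.0025), time origin week 1; residual variance 0.5; AW standard normal; no dropout.

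**3. Scale of the effect.** With V the 12 x 12 covariance of a patient's weekly values, the variance of a Treatment x AW estimate with weekly weights c is 4c'Vc/120. For the mean of weeks 3-11 (mean time 6 weeks from origin):

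- c'Vc = 0.5 + 0.5/9 + 0.0025 x 6² = 0.6456
- SE = √(4 x 0.6456/120) = 0.1467
- full effect δ = (1.960 + 0.842) x 0.1467 = 0.411, which gives that contrast 80% power

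**4. Terms of the piecewise model.** With B the design matrix (intercept, Pre-FD time, Post-FD time) and s the shape of the effect over the weeks, the fitted terms are (B'V⁻¹B)⁻¹B'V⁻¹(δs), with variance 4(B'V⁻¹B)⁻¹/120. Power = Φ(|estimate|/SE − 1.96), plus the negligible other tail.

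**5. The weeks 1-12 mean.** c'Vc = 0.5 + 0.5/12 + 0.0025 x 5.5² = 0.6173; SE = √(4 x 0.6173/120) = 0.1434. The effect is 0.411 x (sum of s)/12. For an effect constant from week 1: 0.411/0.1434 = 2.87, power Φ(0.91) = 0.82. For a step at week 3: 0.411 x 10/12 = 0.3425, ratio 2.39, power Φ(0.43) = 0.67.

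**6. Power of each Treatment x AW term, knot at week 2**

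| Shape of effect | Week-1 level | Pre-FD slope | Post-FD slope | Level at knot | Mean wks 3-11 | Mean wks 1-12 |
|---|---|---|---|---|---|---|
| 0, ½, full from week 3 | .05 | .64 | .09 | .64 | .77 | .71 |
| ⅓, ⅔, full from week 3 | .12 | .34 | .07 | .70 | .78 | .75 |
| Full from week 2 | .05 | .79 | .05 | .79 | .81 | .75 |
| Constant from week 1 | .61 | .05 | .05 | .79 | .81 | .82 |
| Abrupt step at week 3 | .05 | .47 | .23 | .47 | .73 | .67 |
| Onset at week 5, rescaled* | .05 | .10 | .96 | .10 | .75 | .69 |

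*Rescaled by 9/7 so that its average over weeks 3-11 is again 0.411.

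With the knot at week 3, the Post-FD slope has .05-.06 for the first five shapes and .89 for the last; the Pre-FD slope reaches .88 for the step at week 3. If the week-5 onset is not rescaled, the weeks 1-12 mean has 0.411 x 8/12 = 0.274, ratio 1.91, power Φ(−0.05) = .48, against .83 for the Post-FD slope with the knot at week 2.

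**7. At the plan's own effect size.** Take d = 0.60 in high AW, zero in low AW, 25 per cell, AW split in halves, intercept share of variance 0.4 or 0.6. For a benefit held flat over weeks 3-12, power is 0.06-0.11 for the Post-FD slope interaction, 0.12-0.28 for the Pre-FD slope, 0.16-0.28 for both slopes jointly and 0.29-0.31 for the level contrast over weeks 3-12. A benefit that grows over weeks 3-12 gives the Post-FD slope 0.55-0.80.

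**The case against.** A reader might infer that the planned analysis would miss a sustained benefit. The documents do not support that, for these reasons.

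- **The plan never says the Post-FD slope decides.** A piecewise growth model also has lower-order terms. With time zero at the knot, Treatment x AW is a level contrast, with power .64-.79 for the first four shapes above. This stands: the model can carry the effect. But the plan does not designate that term, and its meaning depends on an unstated zero point.
- **Time might be a two-level phase.** Its interaction would then test a change in level (0.21-0.59 at the plan's effect size, for a benefit flat over weeks 3-12). This is possible, although *growth* points to slopes. Under that coding a benefit present from week 1 would still be invisible to the phase interaction (0.05).
- **The follow-up step is opened by any interaction with AW**, not only one involving time, and it then compares arms within strata, as Hypothesis 2 does. This stands. It also means a slope alone would not be the written end of the analysis.
- **The flat shape is an assumption.** Inpatient-plan patients spend 3-4 weeks on the unit, with sobriety checked three times weekly, so a drinking gap can hardly open in weeks 1-2 for them. A late-emerging benefit favours the slope test. This stands, and it also shows that the Pre-FD slope cannot be relied on to carry the effect.
- **The calculation simplifies.** Drinking is assessed daily and binary models are foreseen; the 80% scaling is chosen for comparison. These limit the figures, not the direction.

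A reader might also infer that Treatment is left out of the primary model. Specific Aim 2 and the follow-up contrasts by treatment show that it is intended; it is simply not written into the sentence.

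**Conclusion.** The concern holds as a conditional one. The plan does not state which coefficient tests Hypothesis 2, and the only term it describes concerns change over time, while the hypothesis and endpoints concern drinking over the 12 weeks. If a slope interaction decides, a sustained benefit can be missed.

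Under the assumptions in steps 2 and 3, the Post-FD slope has about 5-9% power for an effect in place by week 3 and then flat, or up to 23% for an abrupt step at week 3. The Pre-FD slope has 5-88%, depending on onset and knot. The weeks 1-12 mean contrast stays at .67-.82 across the tabulated shapes, falling to .48 for a week-5 onset that is not rescaled. These figures compare tests with one another and are not the plan's own power.

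A separate issue remains: at d = 0.60 in high AW, none in low AW and 25 per cell, the interaction has SE √(4/25) = 0.40 and power Φ(0.60/0.40 − 1.96) = 0.32. Naming the right contrast does not cure that.

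**What to change.** 1. Write out the primary model: Treatment, AW, the two time pieces and their interactions, with the time coding, the zero point, the knot and the random effects.
2. State that Hypothesis 2 is decided by the Treatment x AW contrast on model-estimated mean HDD% over weeks 1-12, then DD%. This window matches the endpoint. If a binary model is used, state the scale on which the weekly estimates are averaged.
3. Give the same contrast over the Post-FD weeks as supporting, since that matches the pilot basis of the effect size, and report the Pre-FD and Post-FD slopes as description.
4. Report the treatment effect at mean AW from the same model, to answer the overall efficacy question in Section V, item 1, Statement of Purpose.

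The cost is SAP wording and one contrast statement, on the same data and model. The downside is less power than a slope test for a benefit that emerges only late in treatment.

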The Structured Clinical Interview for DSM-IVTR (SCID, First et al., 1995) will be used to obtain DSM-IVTR Alcohol Dependence and other substance use disorder diagnoses. The SCID's reliability and validity among substance-using populations has been established in large-scale surveys (Kranzler et al., 1996). The number of dependence syndrome elements endorsed from the DSM-IVTR substance abuse/dependence criteria will assess severity of alcohol and other drug dependence. The SCID will also be used to obtain previous psychiatric diagnoses.

Medical History and Physical Examination: All patients will be required to participate in a physical examination including a medical history, electrocardiogram (EKG), blood and urine laboratory assessments prior to initiation of Prazosin to ensure eligibility for Prazosin study protocol. These will be conducted at the CNRU.

Short Form 36 Health Survey (SF-36) is a 36-Item questionnaire used in to assess the subjective quality of life of respondents.

Drug and Alcohol Use Measures:

Addiction Severity Index (ASI: McLellan et al., 1992) is a structured interview that assesses the severity of substance use and substance-related problems in the areas of medical, employment, legal, family/social and psychiatric functioning. The ASI is the most widely used instrument for assessment of substance use and related problems and its psychometric properties are well-established (Cacciola et al., 1997). The ASI will be used at pre-treatment and week 9. Follow-up ASI interviews will be conducted at 30 days post-treatment.

The Substance Use Calendar was developed by Miller and DelBoca (1994) and is based on the Time-Line Follow-Back Method (TLFB) (Sobell, Maisto et al. 1980). The SUC uses a calendar prompt and a number of other memory aids (e.g., holiday, payday, and other personally relevant dates) to facilitate accurate recall of daily drug use during the targeted period. It has demonstrated adequate levels of reliability and validity when administered as an in-person interview, over the telephone, and when administered via computer (e.g. Carey, 1997; Sobell, Brown, Leo, & Sobell, 1996; Sobell, Sobell, Leo & Cancilla, 1988). It's reliability and validity in drug abusing samples has also been established (Fals-Stewart, et al., 2000). In the current study we will use to obtain self-report of day to day use of alcohol and drugs, for the 60 days prior to treatment, weekly during treatment, and at the 30 day follow-up interviews.

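### Pre-treatment drinking is collected for 60 days but enters the primary models only if an arm imbalance turns up; it should be a pre-specified covariate

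*Combined protocol and SAP*

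**What the plan says.** Four parts of the combined protocol and SAP bear on this.

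- **Fixed covariates** (Section V.12, Data Analytic Procedures): "Control variables in all analyses will be gender (0=male), inpatient (0=outpatient), and dropout". Baseline CIWA-Ar enters as a mean-centred continuous moderator.
- **Conditional covariates** (same paragraph): before each analysis, "we will compare the treatment groups on demographic variables, substance use characteristics and previous psychiatric history/predictor variables". Then: "If any group differences are found, the specific variable will be entered as a covariate in all of the specific analyses". No significance level or other threshold is given.
- **Time axis** (same paragraph): withdrawal severity is a "moderator of Time (Pre-Full Dose(FD): weeks 1-2; Post FD: weeks 3-12) were conducted with linear or generalized linear mixed effect (LME/GLME") piecewise growth models. The first outcome period is weeks 1-2.
- **Data collected** (Section V.3, Drug and Alcohol Use Measures): the Substance Use Calendar gives "self-report of day to day use of alcohol and drugs, for the 60 days prior to treatment", and continues through treatment and follow-up.

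The first primary outcome is "Heavy drinking days (5 or more for men, 4 or more for women) during the 12 week period"; the second is any drinking days. The calendar is one of the named sources for both. Hypothesis 2 states them as HDD% and DD% over the 12 weeks.

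**The concern.** A patient's own earlier drinking, measured with one of the instruments that feeds the outcome, is a natural candidate for the strongest baseline predictor of on-treatment drinking. The plan pays for the measurement and leaves its use to chance. CIWA-Ar does not stand in for it, because it measures withdrawal, not consumption.

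The route that is open, a test of baseline difference between randomised arms, selects on the wrong property. A covariate adds precision because it predicts outcome, not because the arms happen to differ on it. The rule also makes the primary model depend on the data, at an unstated threshold.

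At stake is power for differences in drinking level. It matters most in the high-withdrawal patients of Hypothesis 2, where the comparison uses only part of the sample.

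**Working it through.** **Inputs.** From Section V.12, Power Analysis: d = .60, power .80, p < .05 (two-sided assumed), 25 per cell, total 100, recruitment of 120. Table 1 (PRZ/PLA Dosing) shows 75 per arm. The baseline-outcome correlation r is not in the documents and is assumed throughout.

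**The plan's own figure.** For two means at d = .60, n per arm = 2(1.96 + 0.84)²/.60², which gives 44 (45 by exact t), a total of 88-90. A 2x2 F test with f = .30 gives 23 per cell, a total of 92. The stated 25 per cell is therefore not reproduced exactly. With 50 per arm, power for a main effect is .844 by noncentral t. The present point does not depend on this gap.

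**Gain in a linear model.** Residual variance is multiplied by 1 - r². Adjusting is worth a factor 1/(1 - r²) in patients. The standardised effect becomes .60/√(1 - r²). Power below is by noncentral t, two-sided .05.

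| r (assumed) | Variance reduction | Worth in patients | 50 v 50 | 25 v 25 |
|---|---|---|---|---|
| 0 | 0% | 1.00 | .844 | .547 |
| .1 | 1% | 1.01 | .847 | .551 |
| .3 | 9% | 1.10 | .876 | .587 |
| .5 | 25% | 1.33 | .929 | .670 |
| .6 | 36% | 1.56 | .960 | .738 |

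**Allowing for covariates already present.** If baseline drinking correlates a with CIWA-Ar, and CIWA-Ar correlates b with outcome, the relevant quantity is the squared partial correlation (r - ab)²/[(1 - a²)(1 - b²)]. With a = .3-.5 and b = .2-.3 (assumed), r = .3 gives a reduction of 3-7% instead of 9%, and r = .5 gives 18-22% instead of 25%.

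**Does the imbalance rule recover the gain?** Simulation of 4,000 trials per r, 50 per arm, d = .60, entry if the baseline t-test gives p < .05 (assumed):

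| r | Rule fires | Never adjust | Always adjust | Rule |
|---|---|---|---|---|
| .3 | 5.0% | .840 | .867 | .843 |
| .5 | 5.4% | .845 | .934 | .855 |
| .7 | 5.1% | .847 | .988 | .868 |

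**Which estimates gain.** This check used a 12-week piecewise model with N = 100, where r is the correlation with the random intercept. Adding baseline drinking multiplies the standard error of the treatment difference in level over weeks 3-12, at high withdrawal severity, by .96-.97 (r = .3) and .88-.90 (r = .5). For the treatment by withdrawal by time slope the ratio is 1.00. A separate simulation of a treatment by withdrawal difference in level gave ratios of .96-.97 (r = .3) and .87-.90 (r = .5).

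**Binary models.** In one logistic check the treatment coefficient moved from -.52 (SE .43) to -.61 (SE .47). The interval did not narrow, while the ratio of estimate to standard error rose from .52/.43 = 1.21 to .61/.47 = 1.30. The r² formula does not apply here.

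**Withdrawal or prior drinking as the moderator?** In a simulation where only prior drinking modified the treatment effect (by -.4 per SD) and correlated .5 with withdrawal severity, the treatment by withdrawal coefficient was about -.20 (= -.4 × .5). It stayed at -.20 after adding baseline drinking as a main effect, and fell to about 0 only with a treatment by baseline-drinking term.

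**The case against.** The plan does not ignore baseline drinking: substance use characteristics are among the variables compared, and any that differ are added. A reader might infer from the fixed list that baseline drinking can never enter. That is too strong; it can, but by a rule that seldom fires.

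A reader might also infer that the primary comparison is biased. It is not: under randomisation, leaving out a prognostic covariate does not bias the linear treatment contrast.

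The size is uncertain, and this objection stands. No r is given, and features of the trial could lower it: some patients spend 3-4 of the 12 weeks as inpatients, all are alcohol dependent, and Section V.9 ties the start of medication to absence of alcohol. At r = .1 the gain is negligible.

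The 25 v 25 column should not be read as the power of the primary test. The plan treats baseline withdrawal as continuous and makes the median split only after a significant interaction. With 120 or 150 randomised, the halves hold about 30 or 37 per arm, and unadjusted power at d = .60 is .63 or .72.

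Two further inferences are tempting and fail: that adjustment sharpens every treatment by withdrawal estimate, and that it separates withdrawal severity from heavier prior drinking. The slope result and the moderator simulation contradict them.

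Lastly, the plan says the mixed models "were conducted". If outcome analysis had begun when this text was written, adding a covariate would be a post hoc change.

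**Conclusion.** The point holds as one of efficiency. Sixty days of pre-treatment drinking are collected, are absent from the fixed covariates and from the outcome time points, and reach the primary models only through an unspecified imbalance test.

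Pre-specifying them would add power for between-arm differences in drinking level, including a treatment by withdrawal difference in level. In a linear model, residual variance falls by roughly 1%, 9% or 25% at r = .1, .3 or .5, and by somewhat less once CIWA-Ar and the other controls are in. In a binary mixed model the gain comes through a larger conditional effect, not a narrower interval. The treatment by withdrawal by time slope gains nothing. All of this rests on assumed correlations. The case for the change is that the downside is close to nil, not that the gain is known to be large.

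**What to change.** - **Primary models:** name mean-centred 60-day baseline HDD% as a covariate in the heavy-drinking model and baseline DD% in the any-drinking model. Delete covariate selection by baseline significance test.
- **Secondary models:** add the baseline score of each scale where the schedule of assessments confirms that one is collected. The PSQI is described in the text and named as a secondary outcome, but has no row in that schedule, so its baseline timing needs settling first.
- **Moderator question:** add a sensitivity analysis with a treatment by baseline-drinking term, to see whether the withdrawal interaction survives it.
- **Timing:** make the change before outcome data are examined by arm. If that point has passed, keep the planned model and report the adjusted one as a labelled additional analysis.

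The cost is one parameter per primary model and a few lines of SAP text. The primary models need no new data collection.

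### The intent-to-treat models control for dropout, a post-randomisation variable, so average-level treatment contrasts are not the randomised comparison

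*Combined protocol and SAP*

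**What the plan says.** All the modelling text is in Section V, item 12, under Data Analytic Procedures. It states that "Intent-to-Treat (ITT) analyses will be conducted for the clinical outcomes". The primary models, with baseline alcohol withdrawal (AW, the CIWA-Ar score) as a moderator of time before and after full dose, "were conducted with linear or generalized linear mixed effect (LME/GLME) piecewise growth models for continuous and binary outcomes". The controls for all analyses are gender, inpatient status and a three-level code: "dropout (0=completer, 1=dropout/withdrawn prior to 4 weeks, 2=dropout/withdrawn after 4 weeks".

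The plan for the secondary measures is that "linear mixed models with random intercepts will be used to assess the effect of AW, Treatment and Week", and it adds that "All control variables from the main outcome analyses are included in the secondary outcome analyses". A further step is conditional: "If significant interactions with AW are observed for primary or secondary outcome analyses, a median split of AW scores will be conducted", giving treatment contrasts in Low and High AW groups.

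Hypothesis 2 reads: "In high alcohol withdrawal individuals, Prazosin group will show significant reductions in HDD% and DD% during the 12 week treatment period", compared with placebo. The power analysis allows for dropout overall but not by arm: "Including a 15-20% drop-out after enrollment".

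Section V, item 3 (General Procedures) defines drop-out as four missed research appointments in a row. The model's code also counts withdrawal.

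**The concern.** Randomisation makes the arms comparable at baseline. A variable fixed weeks later carries no such guarantee. Once dropout is in the model, the treatment coefficient compares prazosin completers with placebo completers, early dropouts with early dropouts, and so on. If dropout relates both to arm and to drinking, these strata no longer hold like patients.

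The protocol makes both links plausible, without establishing either. Section V, item 3 removes patients who cannot tolerate a minimum dose, after a dose-reduction step. Section V, item 9 (Alcohol Detoxification) withdraws patients who cannot stay abstinent. The Statement of Purpose also lists treatment attendance among the outcomes the drug should improve.

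Three contrasts are exposed:

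- the secondary treatment effects, which no gate precedes;
- any overall 12-week comparison of heavy drinking days or any drinking days;
- the median-split contrasts, if an AW interaction opens them.

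Hypothesis 2 can be read as a comparison of levels or of change over time. Only the level reading is affected. The stake is a result labelled intent-to-treat that shows a benefit that is not there, or understates a real one.

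**Working it through.** **Inputs from the documents.** Dropout is 15-20% overall, with 120 to be recruited for 100 needed (Power Analysis). This is consistent: 100/0.85 = 118 and 100/0.80 = 125. The midpoint, 17.5%, is used below. There are 75 per arm (dosing table) or 60 per arm (half of 120). The planning effect is d = 0.60.

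**Assumed, because the documents are silent.** Dropout by arm; dropout log-odds of +1 per SD of drinking; AW-drinking correlation 0.3; dropouts split evenly before and after 4 weeks; weekly intraclass correlation 0.5.

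**Why the coefficient moves.** Let D be the randomised difference (prazosin minus placebo), d the difference adjusted for dropout, p1 and p0 the dropout proportions on prazosin and placebo, and g the outcome gap between dropouts and completers. Treat early and late dropouts as one group. With dropout as a main effect only, each arm mean is its completer mean plus p × g, so

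d = D − (p1 − p0) × g.

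Under D = 0 there is no bias if p1 = p0 or g = 0. The sign reverses if placebo has the higher dropout.

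A simulation with one summary per patient and no AW terms gave d = -0.13 at 10% v 25%, so g = 0.13/0.15 = 0.87. The formula then gives:

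- 15% v 20%, D = 0: -0.05 × 0.87 = -0.04 (simulated -0.05).
- D = -0.60, dropout driven by drinking only, simulated dropout 21.3% on placebo and 13.7% on prazosin: -0.60 + 0.076 × 0.87 = -0.53 (simulated -0.53 to -0.54).

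**No true effect, 75 per arm, AW and treatment-by-AW terms in the model** (shift and type I error; placebo v prazosin dropout):

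| Level contrast | 15% v 20% | 13% v 22% | 10% v 25% |
|---|---|---|---|
| Weekly continuous, dropout in model | -0.03 SD, 6% | -0.05 SD, 8% | -0.08 SD, 10% |
| Weekly continuous, dropout omitted | -0.01 SD, 5% | -0.01 SD, 5% | -0.01 SD, 5% |
| Weekly binary, dropout in model (true OR 1) | OR 0.93, 7% | OR 0.88, 8% | OR 0.80, 11% |
| Weekly binary, dropout omitted | OR 0.99, 5-6% | OR 0.97, 5-6% | OR 0.95, 5-6% |
| One summary per patient, dropout in model | -0.04 SD, 5% | -0.07 SD, 8% | -0.12 SD, 12% |
| One summary per patient, dropout omitted | 0.00 SD, 5% | 0.00 SD, 5% | 0.00 SD, 5% |
| High-AW half, taken alone, dropout in model | -0.04 SD, 6% | -0.06 SD, 7% | -0.10 SD, 9% |

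Weekly data end at dropout. SD is the weekly SD in the weekly models and the SD of the patient summary in the one-summary model. The Monte Carlo standard error of a 5% rate is 0.2-0.5 points. Repeat simulations of the weekly continuous model gave -0.03, -0.05 and -0.09 SD, with error about 7%, 7-8% and 12%. With 60 per arm, the last two cases give 7% and 9%. At log-odds +0.5 with 75 per arm they give -0.02 SD (5%) and -0.05 SD (7%).

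**Little affected (weekly continuous model).** Treatment-by-phase and treatment-by-AW-by-phase terms shift by 0.00 SD, error 4-5%. Treatment-by-AW shifts by at most -0.02 SD, error 5-6%. The chance that the gate opens and the High-AW level contrast is significant is 1.5-1.9% with dropout in the model and 1.2-1.7% without. One exception appears in the one-summary model: treatment-by-AW error reaches 11-12% if AW is also assumed to raise dropout on prazosin alone.

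**A real effect of -0.60 SD, dropout driven by drinking only** (one summary, 75 per arm): for log-odds 0.5, 1, 2 and 4 the adjusted estimate is -0.58, -0.54, -0.47 and -0.40. Power falls from 97% to 96%, 95%, 91% and 87%.

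Daily-level and log-transformed models were not simulated.

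**The case against.** The strongest reply is that the primary model as written concerns AW moderating change between phases, and those terms barely move. The gated route to Hypothesis 2 adds only a fraction of a percentage point of false positives. This stands, and limits the point to level contrasts.

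Second, the sizes rest on dropout by arm that the documents do not give. At 15% v 20% the error is only 5-7%; at log-odds +1, double figures appear only at 10% v 25%. For craving, anxiety, depression and sleep, the link with dropout is a further assumption. This also stands: harm is possible but not shown.

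Third, where secondary outcomes use Weeks 4, 8 and 12 only, patients lost before week 4 contribute no rows, so removing the covariate cannot restore them. Simulated adjusted shifts are -0.03, -0.04 to -0.05 and -0.08 SD (error 6%, 6-7%, 8-10%). Without dropout they are -0.01, -0.02 and -0.04 SD (5-6%). Removal still helps, but about half the shift can remain.

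Fourth, non-parametric tests of retention and alcohol use are planned, which partly covers reporting dropout by arm. They sit under the laboratory-study heading and do not replace the specified mixed models.

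A pattern-mixture defence fails: that approach needs treatment effects by pattern and averaging over patterns, and neither is specified.

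**Conclusion.** The concern holds. The intent-to-treat label and the dropout covariate cannot both stand for level contrasts. The change in what is estimated follows from the model itself, whatever the data show. The size and direction of any bias cannot be known in advance. They depend on dropout by arm and on how strongly dropout tracks drinking, and with no true effect the bias is nil if either link is absent. Under the stated assumptions the distortion is small at a 5-point imbalance and reaches about 10-12% type I error at 15 points. Treatment-by-time terms are essentially untouched. The laboratory analyses and the non-parametric tests are outside this point.

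**What to change.** Remove dropout from the control variables in every clinical-outcome model under Data Analytic Procedures. Keep gender, inpatient status as fixed at entry, and baseline AW. State that the likelihood-based mixed models assume data missing at random. Report dropout and withdrawal by arm, with timing. Use dropout pattern only in a labelled pattern-mixture or other missing-data sensitivity analysis; for outcomes measured only at Weeks 4, 8 and 12, have it address patients lost before week 4.

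Reconcile the passages that decide who is coded as dropout. Section V, item 3 (Research Plan) and Section VI, A.3 differ on what follows intolerance. Section V, item 9 conflicts with the Outpatient Plan and General Procedures in item 3 on what follows drinking.

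The cost is a change of SAP wording, one extra sensitivity table, and a re-run of any model already fitted, which the past tense in the primary-model sentence suggests may exist. No new data are needed.
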